3.1 Primary Objective

To assess the level of comfort provided by the chin and forehead rest attachment invention when coupled with existing imaging devices, i.e. OCT and Slit Lamp.

3.2 Secondary Objectives

To evaluate the time duration that is needed to adjust for the number of motion artifacts present while using the novel chin and forehead rest attachment when coupled with existing imaging devices, i.e. OCT and Slit Lamp.

4 Study Design and Endpoints

4.1 Description of Study Design

This is a randomized clinical trials study that includes two arms: experimental and control. The purpose of these arms is to compare the medical outcomes in terms of the subject's level of comfort as well as reducing the amount of motion artifacts. Subjects that are willing to participate will be required to participate in both arms.

Because the study design follows routine standard of care, there are no specific safety end points related to this project.

4.2 Study Endpoints

4.2.1 Primary Study Endpoints

Version: 3.0

In order to achieve the primary objective, proving that the level of comfort of the chin and forehead rest invention attached to the existing OCT imaging devices, as opposed to the conventional existing headframes is of a higher caliber, the primary endpoint will be achieved by providing the subject with a questionnaire directly after being imaged and asking two questions: which device, C/N, provided a more comfortable experience, and on a scale of 0-5 to rate the level of comfort, as a result of the headframe, i.e. chin and forehead rest, that the subject experienced while being imaged on either device C/N.

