10.2 Sample Size Determination

Let P1 be the proportion of patients who report improvement of comfort and then P0=1-P1 be the proportion of patients who report no difference between two devices. The primary outcome of interest is to see if P_1 is significantly bigger than 50% or not. With sample size of N=90 subjects, we will achieve 80% power to detect that P1 > 65.7% using a two-sided exact test of proportion with a significance level of 0.05. These results assume that the population proportion P1 under the null hypothesis is 50%.

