10.3 Statistical Methods

Unless otherwise specified, descriptive statistics for continuous variables include the number of patients with data (N), mean, standard deviation (SD), median, minimum, and maximum. The same number of decimal places as in the observed value are presented when reporting median, minimum, and maximum; one more decimal place than in the observed value is presented when reporting mean and quartiles; and two more decimal places than in the observed value is presented when reporting SD.

Categorical data are presented using frequency counts and percentages. All percentages are rounded to one decimal place, unless otherwise specified. Percentages equal to 100 are presented as 100% and no percentages are presented for zero frequencies. Where individual variable values are missing, summaries of categorical data are based on reduced denominators (i.e., the denominators include only patients with available data) and the number of missing values is presented.

The improvement of patient's experience in terms of comfort will be assessed using two-sided exact test of proportion to compare P_1 and P_0 . Further, the comfort levels of each device from all patients will be compared using t test. Linear mixed effect models will be utilized to compare the time duration of adjusting motion artifacts between two devices while accounting for inter-eyes correlations. The p values less than 0.05 will be considered as significant.

10 Source Documents and Access to Source Data/Documents

Source data is all information, original records of clinical findings, observations, or other activities in a clinical trial necessary for the reconstruction and evaluation of the trial. Source data are contained in source documents. Examples of these original documents, and data records include: hospital records, clinical and office charts, laboratory notes, memoranda, subjects' diaries or evaluation checklists, pharmacy dispensing records, recorded data from automated instruments, copies or transcriptions certified after verification as being accurate and complete, microfiches, photographic negatives, microfilm or magnetic media, x-rays, subject files, and records kept at the pharmacy, at the laboratories, and at medico-technical departments involved in the clinical trial. It is acceptable to use CRFs as source documents. If this is the case, it should be stated in this section what data will be collected on CRFs and what data will be collected from other sources.

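### Sections 4.2.1 and 10.2 disagree on whether the comfort rating is primary, and no rule says which of two unadjusted 0.05 tests decides the trial

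*Combined protocol and SAP*

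**What the plan says.** - Section 4.2.1, under the primary endpoint heading, has the subject complete a questionnaire after imaging, "asking two questions: which device, C/N, provided a more comfortable experience, and on a scale of 0-5 to rate the level of comfort". It does not say whether one answer or both must favour the novel headrest.
- Section 10.2 narrows this to one outcome: "The primary outcome of interest is to see if P_1 is significantly bigger than 50% or not". The sample size rests on that outcome alone, "using a two-sided exact test of proportion with a significance level of 0.05".
- Section 10.3 tests the preference proportion and then adds: "Further, the comfort levels of each device from all patients will be compared using t test". It does not say whether the t test is paired. The threshold for every test is the same: "The p values less than 0.05 will be considered as significant".
- The Protocol Summary lists the exact test and the t test side by side, without rank.
- The rating is listed as secondary nowhere. Sections 3.2 and 4.2.2 cover time durations only.
- No testing order, alpha split, multiplicity adjustment or rule for discordant results appears anywhere.

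**The concern.** The statistical section treats preference as the primary outcome, but the endpoint section gives the rating the same standing. If the preference test failed and the rating gave p<0.05, section 4.2.1 would let the sponsor report the primary endpoint as met, and section 10.2 would not. The comfort hypothesis in 10.1 is worded broadly enough to be claimed from either test.

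The two answers can disagree. A subject asked which device was more comfortable may name one and still rate both equally. Both outcomes are subjective, and the subject can tell which headrest is in use. The questionnaire data are also reviewed cumulatively every two months by a group that includes the investigator (section 8.1.1). In that setting the deciding question should be fixed in advance.

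**Working it through.** **Inputs from the documents.** Alpha is 0.05 for each test, and the preference test is a two-sided exact test (10.2, 10.3). The null proportion is 50% (10.2). N is 90 in 10.2 and 150 in section 5, so both are shown. Every subject uses both devices: "Subjects that are willing to participate will be required to participate in both arms" (4.1). The two tests are therefore correlated.

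**Assumptions not in the documents.** These are a 50/50 split of preference answers under no difference, the spread of the ratings, the correlation between the two answers, and whether the t test is paired.

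**Step 1: the plan's own power figure.** Section 10.2 says "With sample size of N=90 subjects, we will achieve 80% power to detect that P1 > 65.7" per cent. At N=90 the exact test rejects at 55 or more (or 35 or fewer) of 90, because 2 × P(X≥55 | 90, 0.5) = 0.0446, while a cut-off of 54 would give 0.0725. Power is P(X≥55 | 90, 0.657) = 84.8%, not 80%. The stated 65.7% corresponds to 85% power (65.74%), and 80% power corresponds to 64.8%. The mismatch is in the conservative direction and does not affect the error-rate question.

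**Step 2: P1 as sole primary.** The two-sided size is 4.46% at N=90 and 4.09% at N=150 (cut-off 88). By symmetry, half of each favours the novel device: 4.46/2 = 2.2% and 4.09/2 = 2.0%.

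**Step 3: limits if either test suffices.**
- Upper bound under any dependence: 0.05 + 0.05 = 10%.
- Independent tests at full size: 1 − 0.95² = 9.75%.
- Independent, with the exact test's real size: 1 − (1 − 0.0446)(0.95) = 9.2% at N=90, and 1 − (1 − 0.0409)(0.95) = 8.9% at N=150.

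**Step 4: allowing for correlation.** For two correlated normal statistics, the rate is 1 − P(|Z1|<1.96 and |Z2|<1.96):

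| Correlation | Two-sided, either test | Favouring the novel device |
|---|---|---|
| 0 | 9.75% | 4.94% |
| 0.5 | 9.07% | 4.54% |
| 0.7 | 8.35% | 4.17% |
| 0.8 | 7.81% | 3.90% |
| 0.9 | 7.04% | 3.52% |

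**Step 5: simulated null trials.** The exact test was applied to preference and a t test to rounded 0-5 ratings from the same subjects.
- Paired t test, 20,000 trials per setting, N=90 and 150: 7.3-9.4% two-sided and 3.5-4.8% favouring the novel device. The correlation of the two statistics ran from 0.22 to 0.78. The Monte Carlo standard error is about √(0.08 × 0.92 / 20,000) = 0.2 points.
- Paired t test, rating-difference SD about 1.5, 40,000 trials per setting. At N=90: 9.2% with unrelated answers, 8.7% at latent correlation 0.7 and 7.3-8.0% at 0.9-1.0. At N=150: 8.9%, 8.1% and about 7.5%.
- Unpaired t test where each subject's two ratings share a subject effect: 4.2-5.4%, because that test alone then rejects only about 0.7-0.9% of the time. Without a shared effect, it behaves like the paired test (7.4-9.3%).

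**Step 6: if both tests must succeed.** The rate cannot exceed 5%, and in the simulations it was at most 2.0%. The plan gives no power for that joint requirement.

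**The case against.** The strongest reply is that section 10.2 already settles the matter. It names one primary outcome and powers only that one, and 10.3 brings in the rating afterwards with *Further*. On that reading the error rate is 4.1-4.5% and nothing is inflated. If both answers must succeed, the rate is also controlled. Only one of three readings inflates the error, and the documents do not state it.

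Most of this stands as a limit on the size of the problem. A reader might infer that the chance of a false primary claim is well above 5%. The documents do not support that as a flat statement, for four reasons:
- It needs an either-test rule that is permitted but not written.
- It needs a paired t test, which 10.3 does not specify.
- The highest figures need near-independent answers, which is implausible when the same subjects answer both questions about the same experience.
- It counts results in both directions. False claims for the novel device, the claim that 4.2.1 aims at, stay below 5%. The proper comparison for that direction is 2.5%, however, and 3.5-4.8% exceeds it.

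The 50/50 null is also an assumption. Section 10.2 defines the complement of P1 as patients reporting no difference, so such an answer may be allowed, and the questionnaire is a separate attachment.

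The reply does not remove the conflict. The rating's only listing as an endpoint is under the primary heading in 4.2.1, and it fits the primary objective in 3.1 at least as well as the choice does. *Further* is a connective, not a testing order, and the Protocol Summary omits it. If 10.2 governs, 4.2.1 is wrong as written.

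**Conclusion.** The concern holds as an unresolved conflict over the primary endpoint, with a conditional effect on the error rate. It should be corrected before analysis because it changes what the trial may claim.

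If either test suffices and the t test is paired, the two-sided false-positive rate is about 7-9%, with a ceiling of 10%. In favour of the novel device it is about 3.5-4.8% against a nominal 2.5%. These figures rest on a 50/50 null, a rating-difference SD of about 1.5 and the correlation ranges shown, none of which the documents give. With an unpaired t test and a shared subject effect the two-sided rate is about 4-5%. With P1 as sole primary it is 4.5% (N=90) or 4.1% (N=150). It would be wrong to conclude that the sponsor plans to claim success on either test. The text leaves that route open and does not adopt it.

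**What to change.** In section 4.2.1, name the preference proportion P1 as the only primary endpoint, matching 10.2. Move the 0-5 rating to first secondary endpoint. In section 10.3, state that the rating is tested for confirmation only if the P1 test is significant. Otherwise, report the mean within-subject difference with its 95% CI as descriptive. Align the Protocol Summary.

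The change costs wording only. P1 keeps the full 0.05, so its power at 65.7% stays at 84.8% (N=90) or 97.0% (N=150). Splitting alpha at 0.025 would also control the error, but would lower these to 72.3% and 93.9%. Requiring both tests would control it too, but needs a power calculation that the plan does not have. The downside of the proposed change is that the rating alone can no longer carry a positive primary claim.

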4.2.2 Secondary Study Endpoints

A secondary objective includes evaluating various time durations while a patient is being imaged to determine whether the amount of motion artifacts are in fact being reduced by implementing the invention to existing devices. In one of the standard clinical OCT imaging devices, the Cirrus OCT, there is an eye tracking mode that can be activated whilst imaging a patient. This feature selects a specific location within the eye and will constantly adjust, i.e. track, for the fine fixation adjustments that occur when a patient's eye is moving very slightly. Therefore, in order to view whether there are a higher number of motion artifacts found in one image versus another, the Imager can time the duration it takes from the moment that they click "acquire", to when the progress bar is full. This is because the more time it takes for the system to fully acquire an image it directly correlates to how still the subject's eye is. Additionally, the data acquisition time can also be affected by whether the Imager is able to acquire a clear fundus photo, i.e. when there are no media opacities as well as if the Imager properly corrects for the refractive error.

5 Study Enrollment and Withdrawal

We aim to enroll 150 total subjects including healthy volunteers and subjects that have an existing eye disease including, but not limited to, glaucoma, AMD, DR, and CSCR. The site can actively enroll new subjects and these subjects will be are continuously followed in their institute. The total NYU cohort will include 150 healthy subjects as well as any eye related disease suspect subjects. There will be no enrollment restrictions based on gender, ethnic origin or HIV status and the study population will reflect the demographics of NYU Department of Ophthalmology. Subjects from clinical groups will participate in all applicable sub-studies of the protocol.

Subjects will be included in both groups, labelled as either Group 1 (Novel) or Group 2 (Conventional). Both groups will include subjects that are identified with glaucoma, age related macular degeneration, diabetic retinopathy, and central serous chorioretinopathy or any other eye related disease as well as healthy volunteers that are recruited from the clinic that undergo the clinical examination as part of their routine clinical management and healthy volunteers that are invited to the clinic to undergo the clinical examination for the purpose of the study.

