| Title | Comfortable and Stabilizing Chin & Forehead Rest Attachment for Slit Lamp Configurations |
|---|---|
| Short Title | Invention Study |
| Brief Summary | Cohort will consist of 150 subjects consisting of those that are healthy or have an existing eye disease. Subjects will be imaged on two OCT devices: device N, invention attached to the device and device C, the standard conventional device. The Imager will time multiple durations, one of them which will act to evaluate the number of motion artifacts that arise due to both the instability and lack of comfort the patient is experiencing in that particular moment. Following the imaging session, subject will be asked which device was more comfortable. |
| Phase | NA |
| Objectives | The primary objective is to ascertain that the OCT Imaging device with the invention attached provides a more comfortable experience for the subject. While the secondary objective is to reduce the time it takes for the system to account for the number of motion artifacts. |
| Methodology | Randomized |
| Study Duration | Until target number of subjects is reached |
| Participant Duration | One clinic visit |
| Duration of IP administration | One clinic visit |
| Study Sites | NYU Department of Ophthalmology |
| Number of participants | 150 subjects |
| Description of Study Agent/Procedure | Comfortable chin and forehead rest that can be adjusted to fit each individual's size. |
| Statistical Analysis | Descriptive statistics for continuous variables and categorical data, presented using frequency counts and percentages will be used for group and device comparison. Patient experience will be assessed using two-sided exact test of proportion. Comfort levels of each device will be compared using t test. Linear mixed effect models will be utilized to compare the time duration while accounting for inter-eyes correlations. |

Version: 3.0

Schematic of Study Design

Screening Period

- Total n=150
- · Obtain informed consent
- Screen potential subjects by inclusion and exclusion criteria
- Obtain history, document

Day of Imaging

1. Randomize Order of Devices

 Provide clinic with 150 envelopes in which they are assigned with instructions regarding which device and eye the Imager should begin with (C/N & OS/OD)

2. Study Intervention

- Measure the length of the subject's face
- Provide subject with questionnaire containing the following
 - o Are you feeling well?
 - o Are you feeling tired today?
 - o Are you uncomfortable?

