6.1.5 Administration

The order in which a subject will be imaged on either OCT imaging device C/N and whether the Imager will begin with either the OD/OS eye will be randomized. This will be done by providing the NYU Ophthalmology Clinic with a total of 90 envelopes that the Imager will choose from a mixed pile in which they will be evenly divided with a message to begin with device C/N and to begin with eye OD/OS.

The Standard Operating Procedure as to how to operate the novel device for imaging a subject can be seen below:

Version: 3.0

- 1. Sanitize chin and forehead rest
- 2. Seat subject by device
- 3. Move chinrest to either OD/OS
 - a. Slide chinrest to either right/left side
- 4. Size chinrest
 - a. Subject should place their chin in the rest and technician should either pull apart/push together the chin rest to either make it larger/smaller to fit the patient
- 5. Size mount of chinrest
 - a. Pull apart the mount easily to allow for the chinrest's length to be extended
- 6. Lock extension
 - a. Rotate knobs on both sides
- 7. Find correct/comfortable angular position of the chinrest
 - a. Push/move chinrest to position that it is comfortable i.e. not protruding into subject's neck and subject feels relaxed
- 8. Lock rotation
 - a. Tighten the bolt placed around the ball joint
- 9. Subject should rest forehead against the rest
- 10. Technician /imager should check if subject has to be adjusted closer to the device (based on the image from the device)
 - a. push/pull forehead rest by side of device so it will be adjusted along the grooved slot
- 11. Size forehead rest
 - a. tighten/loosen the strap on the side of the forehead rest to either make it smaller/larger for the patient (it will automatically lock into place)
- 12. Check if subject is comfortable, adjust if need be
- 13. Image subject according to scan protocol

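### Acquisition time is measured by an Imager who sees the headrest and whose focusing affects it; the supplied text does not equalise that focusing between N and C, so a consistent handling difference would bias the comparison

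*Combined protocol and SAP*

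**What the plan says.** Section 4.2.2 makes acquisition time the measure of motion artifacts. For this, "the Imager can time the duration it takes from the moment that they click" the acquire button to the moment the progress bar is full. The Protocol Summary agrees: "The Imager will time multiple durations, one of them which will act to evaluate the number of motion artifacts". Section 4.2.2 then names two other influences on the same time. One is whether a clear fundus view is obtained: "the data acquisition time can also be affected by whether the Imager is able to acquire a clear fundus photo". The other is operator performance: "as well as if the Imager properly corrects for the refractive error".

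On who does the work, Section 6.1.5 has the Imager draw the envelope that names the starting device and eye. The operating procedure written out there is for N only: "The Standard Operating Procedure as to how to operate the novel device for imaging a subject can be seen below". It includes fitting the rest to the subject and repositioning the subject from the live image. No matching steps are written for C.

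Section 7.2 fixes the scans (one macula and one optic nerve head image per eye) and says nothing about the focus setting. Sections 2.3 and 6.1.5 randomise device order and eye order. Section 10.3 compares the times with a linear mixed model whose only stated adjustment is for correlation between eyes, with significance at 0.05.

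**The concern.** The time is meant to show how still the eye is. By the protocol's own account it also reflects how well the Imager has focused, and the Imager both takes the measurement and can see the headrest. If the Imager focuses more carefully, or starts or stops the timing differently, on one device than on the other, that difference goes straight into the N minus C contrast.

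The design protects against part of this. Each subject is imaged on both devices (Section 4.1), so fixed eye characteristics such as media opacity cancel. Randomised order balances fatigue, practice and other effects of being first or second. Neither removes a handling difference that goes with the headrest itself, because it has the same sign whichever device comes first.

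At stake is the interpretation of the only secondary objective (Section 3.2), for which Section 10.1 states its own hypothesis. A shorter time on N would be reported as fewer motion artifacts when part or all of it could be focusing or timing.

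**Working it through.** **The plan's own figure.** There is none for this endpoint: no SD, effect size or sample size is given for acquisition time. The one power statement (Section 10.2: N=90, 65.7% against 50%, 80% power) concerns comfort. The exact two-sided test there rejects at 55 or more of 90 and has 84.8% power, which is above the stated figure and does not bear on this point.

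**Inputs.**
- N = 90 (Sections 2.3, 6.1.5, 10.2) and N = 150 (Protocol Summary, Section 5). The documents use both.
- Two-sided 0.05, critical value 1.96 (Section 10.3).
- Four scans per device: two eyes, two scans each (Section 7.2). They are averaged to one N minus C difference per subject, assuming complete data and a model that respects the pairing.
- Assumed: no true device effect on motion, and a constant handling shift b.
- Assumed: SD s of the subject-level mean difference.

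**Formula.** SE = s/√N. The chance of a significant result is Φ(b/SE − 1.96) + Φ(−b/SE − 1.96).

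**Step 1: SD units, so that no value in seconds is needed.**

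| Shift b/s | N=90 | N=150 |
|---|---|---|
| 0 | 5% | 5% |
| 0.1 | 16% | 23% |
| 0.2 | 47% | 69% |
| 0.3 | 81% | 96% |

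Simulated one-sample t tests (20,000 runs per cell) agree within about one percentage point: 15.6%, 46.9% and 80.8% at N=90; 22.7%, 68.2% and 95.4% at N=150.

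The shift giving a 50% chance is 1.96/√N: 1.96/√90 = 0.21 SD and 1.96/√150 = 0.16 SD. For 80% it is (1.96 + 0.84)/√N: 0.30 SD and 0.23 SD. The larger trial is the more easily misled, because its SE shrinks while the bias stays.

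**Step 2: seconds, for an illustrative shift of 0.2 s.**

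| Assumed s | b/s | N=90 | N=150 |
|---|---|---|---|
| 0.5 s | 0.40 | 97% | 99.8% |
| 1 s | 0.20 | 47% | 69% |
| 2 s | 0.10 | 16% | 23% |
| 5 s | 0.04 | 6.7% | 7.8% |
| 10 s | 0.02 | 5.4% | 5.7% |

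Example, N=90 and s=2 s: SE = 2/√90 = 0.21 s, b/SE = 0.95, and Φ(−1.01) + Φ(−2.91) = 0.16. With a 0.1 s shift and s from 0.5 to 2.0 s, the ranges are 8%-48% (N=90) and 9%-69% (N=150).

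**Step 3: which differences count as b.** Only a difference with the same sign on every N-versus-C comparison does. Random variation in focusing or reaction time has mean zero and enlarges s. Differences that follow session order fall on N and C about equally under randomised order.

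**The case against.** Four points stand, and they limit the concern.

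- **Silence is not proof.** A reader might infer that focus is in fact unequal between devices, or that a stopwatch is used. The documents support neither. Section 4.2.2 names no timing method. Section 6.1.5 refers to a scan protocol and Section 13.3 to a Manual of Procedures; neither is among the supplied documents, and either could specify focus settings. What can be said is that the supplied text does not specify them. A rule that protects an endpoint still belongs in the protocol, and neither document is in the Section 17 list of attachments.
- **Not all operator variation is bias.** A reader might infer that any lapse in focusing or timing distorts the result. As Step 3 shows, only a consistent device-linked difference does. The documents name no mechanism that would make focusing systematically better on one headrest. The nearest is that image-based repositioning is written down for N alone.
- **One Imager per subject is already the natural reading.** Sections 5.5 and 6.1.6 describe a single imaging session, and one envelope instructs one Imager. Even if Imagers changed, nothing ties an Imager to a device.
- **Timing leaves little room for judgement.** Start and stop are on-screen events, so error is probably limited to reaction time and largely cancels within a subject. Focusing is the stronger route.

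It could also be argued that easier focusing is a genuine benefit of N. That does not rescue the endpoint as defined, because Section 4.2.2 interprets the time as stillness of the eye.

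**Conclusion.** The concern holds in a limited form. The secondary endpoint is timed by someone who sees the headrest, and the protocol says that person's focusing changes it. The supplied text neither equalises focusing between N and C nor adjusts for it. A consistent handling difference of about 0.21 SD (N=90) or 0.16 SD (N=150) would give an even chance of a false device result.

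Whether that is a small difference in seconds cannot be known from the documents. The high percentages in the seconds table need an SD at the low end of an assumed range; at 5 s or more, a 0.2 s shift leaves the error rate near nominal. A reader might take 97% or 99.8% as the expected false-positive rate. They are the extreme end of a sensitivity range in which both the shift and the SD are assumed.

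The change is worth making because it is cheap and makes a time difference easier to attribute to the headrest. The primary comfort endpoint is unaffected.

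**What to change.** **Section 7.2.** Set and record the focus (refractive) correction for each eye at the first session, start the second device from the same value, and record any change on the CRF. It should be a starting value and not a locked one, because N can move the subject relative to the instrument and a first-session error should not be carried over by rule. State that the same Imager does both devices for a subject.

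**Section 4.2.2.** Take the duration from the instrument's log or a screen recording of the acquisition window where available. The documents do not show that either exists, so add a fallback: otherwise keep the click-to-full-bar timing and report it as unmasked operator timing.

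**Cost.** One CRF field, a few lines of text and some existing staff time to read off durations. No extra visits or subjects are needed.

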2.1 Background Information and Relevant Literature

Currently in Ophthalmological Offices, patients that are being imaged on OCT devices often do not have a comfortable patient experience. They tend to move away from the device in order to stretch every so often and oftentimes complain about it. This adds additional time to the imaging process, thereby extending the wait time for the following patients. Furthermore, due to the lack of ability to adjust the chin and forehead rest components to each individual patient's size, the patients tend to move around quite a bit which both lengthens the time, as previously mentioned, as well as increases the likelihood of artifacts, which lead to the misdiagnosis of Glaucoma. This is a catastrophic pitfall as 3 million Americans have Glaucoma, which is the "second leading cause of blindness worldwide. Additionally, there are 43 million people worldwide that suffer from blindness and 77% of those cases could have possibly been prevented by reducing the number of artifacts in their scans. To summarize, the purpose of this invention is to solve the problem in which patients are potentially being misdiagnosed or undiagnosed with ocular diseases as a result of patient discomfort induced movement and subsequent diagnostic testing artifacts which could prevent an efficient intervention to be enacted thereby reducing the patient's chances of suffering from a debilitating eye disease.

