6.1.6 Duration of Therapy

The duration of therapy includes one imaging session in which the subject is imaged on both device A and B for both eyes and has 1 scan of their Macula and 1 scan of their ONH acquired.

For the second objective, an evaluable participant should be consistent with Section 10, Statistical Considerations and/or Statistical Analysis Plan (SAP) which will include the minimum time duration it can take for an image to be acquired which can provide a result yielding in a statistically significant value.

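### The only motion measure is the time from the acquire click to a full progress bar; aborted and repeated attempts are not recorded, so a device difference can be understated if attempts are lost more often on one headrest

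*Combined protocol and SAP*

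**What the plan says.** The Protocol Summary states: "The Imager will time multiple durations, one of them which will act to evaluate the number of motion artifacts". Section 4.2.2 likewise speaks of "evaluating various time durations while a patient is being imaged", but defines only one of these durations, the one that starts when the "Imager can time the duration it takes from the moment that they click" acquire and stops when the progress bar is full. It treats a longer time as a sign of a less steady eye. The measure relies on the instrument's tracker, of which the section says "there is an eye tracking mode that can be activated whilst imaging a patient"; it does not require tracking to be on.

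Section 6.1.6 says that each subject "has 1 scan of their Macula and 1 scan of their ONH acquired", for both eyes and both devices, and Section 7.2 repeats one image per region per eye. Section 10.3 compares the durations with a linear mixed model that allows for correlation between eyes. Section 6.1.6 leaves the definition of an evaluable participant for this objective to Section 10, which contains none.

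Section 2.1 describes the problem to be solved. Of patients being imaged it says: "They tend to move away from the device in order to stretch every so often and oftentimes complain about it". Section 4.1 gives the purpose of the comparison as "level of comfort as well as reducing the amount of motion artifacts".

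**The concern.** The rationale in Section 2.1 is about patients who leave the headrest. The clock in Section 4.2.2 is built on fine eye movement that the tracker can follow. If a subject pulls back during an acquisition and the attempt is abandoned, the bar does not fill and the literal rule yields no time for it. Such losses depend on the outcome itself, and they would be expected more often on the less stable headrest. Dropping them could hide a benefit of the novel headrest, or a harm if it is the less stable one.

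This clock is also the only planned evidence on motion. Participation is a single session with no follow-up (Section 5.5), so attempts not noted on the day cannot be recovered later.

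**Working it through.** **What the text settles and what it leaves open**

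- *Motion within a running scan:* captured, because tracking delays lengthen the interval (4.2.2).
- *Attempt aborted before the bar fills:* no duration under the literal definition. The text does not say whether the clock restarts at the next click or runs on from the first.
- *Scan that fills the bar but is then rejected:* it has a time, but the plan does not say which time is entered. The timed scans have no acceptance standard; the only motion limit, in Section 5.1, concerns the OCT used to establish glaucoma eligibility.
- *Scan never obtained:* no rule in Section 10.3.
- *Number of attempts:* not recorded in Sections 4.2.2, 6.1.6 or 7.2, nor in the Schedule of Events, which lists only the imaging step.

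**Size**

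There is no plan figure to reproduce. Section 10.2 gives power only for the comfort preference, and no mean, SD, effect or failure rate is stated for acquisition time. The following illustrates direction only, and every input is an assumption:

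- Interruptions per attempt, K, are Poisson with mean 3 on C and 2 on N.
- A completed scan takes 10 + 3K seconds.
- An attempt is abandoned when K exceeds m, costs 5 + 3(m+1) seconds, and is repeated until one succeeds.

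Formulas: completed-scan mean = 10 + 3·E[K | K ≤ m]; lost attempts per scan = 1/P(K ≤ m) − 1; total time = completed-scan mean + lost attempts × cost.

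*No attempt abandoned.* C: 10 + 3×3 = 19. N: 10 + 3×2 = 16. Both measures differ by 3.0 s.

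*m = 4.*
- E[K | K ≤ 4] is 39/16.375 = 2.382 (C) and 12.667/7 = 1.810 (N).
- P(K ≤ 4) is 16.375·e⁻³ = 0.8153 and 7·e⁻² = 0.9473, so lost attempts are 0.2266 and 0.0556 per scan.
- Each lost attempt costs 5 + 3×5 = 20 s.

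*m = 2.*
- E[K | K ≤ 2] is 12/8.5 = 1.412 and 6/5 = 1.200.
- P(K ≤ 2) is 8.5·e⁻³ = 0.4232 and 5·e⁻² = 0.6767, so lost attempts are 1.3630 and 0.4778 per scan.
- Each lost attempt costs 5 + 3×3 = 14 s.

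| Abandoned when K exceeds | Completed-scan time C / N (s) | Difference (s) | Total time C / N (s) | Difference (s) |
|---|---|---|---|---|
| never | 19.00 / 16.00 | 3.00 | 19.00 / 16.00 | 3.00 |
| 4 | 17.15 / 15.43 | 1.72 | 21.68 / 16.54 | 5.14 |
| 2 | 14.24 / 13.60 | 0.64 | 33.32 / 20.29 | 13.03 |

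The last row is extreme: it implies that 58% of attempts on C and 32% on N are abandoned (1 − 0.4232 and 1 − 0.6767). The pattern is what matters. With no losses the two measures agree; as losses rise and differ by device, the completed-scan difference shrinks while the total-time difference grows.

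**The case against.** **The exclusion is inferred.** A reader might conclude that the plan discards lost attempts and restarts the clock. It says neither; timing from the first click to an eventual full bar also fits the words. This stands, and it limits the point to what the literal text leaves unrecorded. Silence is still a gap, because Imagers could time repeats differently.

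**The clock fits the stated objective.** Section 3.2 asks how long it takes to adjust for motion, and Sections 10.1 and 10.3 test that duration. This stands too, and is a reason to keep the measure. But Sections 4.1 and 4.2.2 go on to claim fewer artifacts, which a time alone does not establish.

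**Section 2.1 does not place the movement.** Patients may stretch between scans and not during acquisition. That is correct, so how often attempts are lost cannot be known from the documents.

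**Confounding.** Section 4.2.2 says media opacities and refractive correction also affect the time, which might suggest a biased comparison. Each subject is imaged on both devices in randomised order, so opacities are shared. Only the Imager's correction could differ between devices, and nothing indicates that it does.

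**Total time has its own fault.** Section 6.1.5 lists sizing, locking and positioning steps for N, so re-seating may take longer there. Suppose 10 s per completed scan, attempts lost on 10% of scans with N and 20% with C, and a lost attempt costing 60 s on N and 30 s on C (all assumed). Then N takes 10 + 0.10×60 = 16 s and C takes 10 + 0.20×30 = 16 s: half the losses on N, and no saving in time. This stands. It is why total time should sit beside the existing clock, with the attempt count, and not replace it.

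**Conclusion.** The gap is real and its effect is conditional. The single defined motion measure covers completed acquisitions if read literally, and no part of the plan records attempts, repeats or scans never obtained. If losses differ between headrests, the measure can understate the device difference, in whichever direction it lies. No size can be given without a loss rate; the figures above show direction on assumed inputs, and with no losses there is no bias.

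Two stronger readings are not supported. One is that the measure ignores motion: tracking delays within a scan do count. The other is that the time result must be biased toward no difference: that requires lost attempts, and losses that differ by device. The point concerns a secondary endpoint only and leaves the comfort result untouched, but it should be settled before enrolment because the missing data cannot be rebuilt.

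**What to change.** In Section 4.2.2 and on the CRF:

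1. Keep the acquire-to-full-bar time and its mixed model.
2. For each eye, scan type and device, also record the number of acquire clicks, the reason for each failed attempt, and the total time from the first click to the full bar of the final scan.
3. In Section 10.3, compare attempts and total time between devices alongside the existing model, and report scans never obtained by device.
4. Require eye tracking to be on for every timed scan on both N and C.
5. State the conclusion as acquisition time and attempts under tracking, not as a reduced number of motion artifacts.

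Cost: with 2 devices, 2 eyes and 2 scan types there are 2×2×2 = 8 timed scans per subject, so two added numbers per scan make 16 short entries, plus a reason where an attempt fails. The Imager and the stopwatch stay the same. Total time will include re-seating and repeats for blinks or operator error; the recorded reasons let these be described.
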